12.8.1 Sponsor medical assessment

The sponsor has delegated the responsibility for oversight of IMP safety profile and medical assessment of AEs, ARs, SAEs and SUSARs to the CI as medical assessor.

The CI must review all SAEs within 72 hours of receipt. This review should encompass seriousness, relatedness, and expectedness. Day 0 for all SUSARs is when the SAE / SUSAR is received by the CI and / or coordinating team and / or sponsor (whichever is first).

It is noted that the CI cannot downgrade the PI assessment of an event's causality. If there is disagreement between CI and PI assessment, no pressure should be placed on the PI to alter their assessment, but the CI can liaise with the site PI before the CI's final decision. The CI and PI assessment can differ.

12.8.2 Procedures for reporting blinded SUSARs

As a regulatory requirement, all SUSAR reporting to the MHRA and REC should be performed in an un-blinded manner. Investigators will only receive blinded information unless un-blinded information is judged necessary for safety reasons. The site PI should only un-blind the treatment allocation during the trial if this is relevant to the safety of the subject. With regards to the Sponsor, when an event which is a SUSAR, the blind should be broken by the sponsor only for that specific child, via the online randomisation/unblinding system.

The blind should be maintained for persons responsible for the ongoing conduct of the study (such as the site PI and sub-investigators, research nurses, study co-ordinators, data managers, pharmacists) and those responsible for data analysis and interpretation of results at the conclusion of the study, such as the statistician. Un-blinded information should only be accessible to those who need to be involved in the safety reporting to national competent authorities, Ethics Committees and IDMC, or other persons performing ongoing safety evaluations during the trial.

The CI, as sponsor medical assessor, will assess the event blinded for all possible IMPs, placebos, and combinations.

12.9 URGENT SAFETY MEASURES

The CI may take urgent safety measures to ensure the safety and protection of the clinical study participants from any immediate hazard to their health and safety, in accordance with Regulation 30 of the Medicines for Human Use (Clinical Trials) regulations. The measures should be taken immediately. In this instance, the approval of the Competent Authority prior to implementing these safety measures is not required. However, it is the responsibility of the CI to attempt, where possible, to discuss the proposed change with the sponsor and Medical Advisor at the MHRA (via telephone) prior to implementing the change if possible.

The CI has an obligation to inform both the MHRA and Research Ethics Committee in writing **within 3 days** of implementing the Urgent Safety Measure. They must also submit a substantial amendment documenting the changes with 14 days of implementing the urgent safety measure. The JRMO must be sent a copy of the correspondence with regards to this matter as soon as it is sent.

13 Annual reporting

13.1 DEVELOPMENT SAFETY UPDATE REPORT (DSUR)

The DSUR will be written by the CI (following Sponsor procedures) and submitted to the sponsor for review prior to submission to the MHRA. The DSUR is due for submission within 60 days of the end of the reporting period. The reporting period is annually from the date on the "Notice of acceptance letter" from the MHRA. The sponsor's delegated Medical Assessor, usually the CI, will carry out a risk benefit analysis of the IMPs encompassing all events having arisen on the study. REC will be sent a copy of the DSUR.

13.2 ANNUAL PROGRESS REPORT (APR)

The APR will be written by the CI (using the HRA's template) and submitted to the sponsor for review prior to submission to the REC. The APR is due within 30 days of the anniversary date of the "favourable opinion" letter from the REC.

14 Statistical and data analysis

14.1 SAMPLE SIZE CALCULATION

Since Razi et al, in a secondary prevention study, reported a 38% reduction in wheeze episodes with oral BV, our effect size is based on a reduction of 40% of the number of children developing parent-reported doctor-confirmed wheeze (22% to 13.2%) [13]. To detect this difference with 90% power at the 5% significance level, we need a total sample size of N=778 children (calculated in Stata using the ssi command). We will recruit 894 children in total from the UK and Australia, which allows for 116 (13%) to be lost to follow-up.

We chose a 40% reduction in the development of wheeze after 24 months of treatment since;

- 1. our parent panel regarded this to be an important and meaningful effect that justifies treating some children who are not going to develop asthma.
- 2. a 40% reduction is compatible with the effect reported in several therapeutic studies of BV. First, as mentioned above, Razi et al demonstrated a 38% reduction in wheezing attacks in the BV-treated group of infants [13]. Second, Esposito et al in a retrospective matched analysis of children receiving oral BV for 2 years reported a 50% reduction in risk of new respiratory tract episodes [24]. Third, Gutiérrez-Tarango et al reported a 37% reduction in acute respiratory tract infections in a trial of children 1 to 12 years of age who were randomized to receive either OM-85 BV or placebo at the beginning of the trial, and then at 6 months later using the same schedule [30].
- a 58% reduction in development of wheeze reported for raw milk in the recent metaanalysis of Brick et al, and a 40% reduction is compatible with effect of asthma therapies in active preschool wheeze [31]. The Prevention of Asthma in Kids (PEAK) Trial 45 randomised children 2 to 3 years of age without wheeze to either daily inhaled fluticasone propionate or placebo for 2 years. After 2 years, study therapy was discontinued, and children were followed for an additional year to determine wheeze. Although the proportion of episode-free days during the 3rd year of the study did not differ between treatment groups in the PEAK trial (i.e. there was no disease modifying effect of inhaled steroids), during active treatment inhaled steroid-treated children had a 34% reduction in wheeze exacerbations [32].

14.2 PLANNED RECRUITMENT RATE

Power calculations are shown in section 14.1 above and an overview of recruitment is also covered in section 3.

Recruitment will take place over an 18-month period with particular focus on the two winter seasons within this timeframe. Winter hospital admissions for bronchiolitis in children in the 3 to 12 months age range for the five UK study sites are; n=406 for Barts Health, n=229 for King College, n=396 for Edinburgh, n=153 for Aberdeen and n=263 for Southampton; total n=1,447.

With recruitment continuing over a Summer/Spring season and two winter seasons gives a conservative estimate of n=2894. With a sample size of 894, the recruitment rate is therefore 31%.

In the winter seasons, for the months September through to February we assume a realistic recruitment rate of 17 patients at each of the five UK sites. For the months March through to August we assume a recruitment rate of one child per site.

14.3 END OF TRIAL (EOT) DEFINITION

EOT is defined as three months after the Last Participant Last Visit (LPLV).

The CI is delegated the responsibility of submitting the EOT notification to REC and MHRA once reviewed by the sponsor. The EOT notification must be received by the REC and MHRA within 90 days of the end of the study. If the study is ended prematurely, the Chief Investigator will notify the Sponsor, REC, and MHRA within 15 days, including the reasons for the premature termination.

14.4 STATISTICAL ANALYSIS PLAN

To maintain blinding for any interim reports an independent statistician will prepare any information which requires knowledge of treatment allocations.

A full detailed statistical analysis plan will be developed prior to final analysis. The purpose of this document is to provide details of the statistical analyses and presentation of results to be reported within the principal paper(s) of the trial. Any exploratory, post hoc or unplanned analysis will be clearly identified as such in the respective study analysis report.

The trial statisticians conducting statistical analysis work will be blinded in relation to allocation status until the SAP is signed off, all follow up data is collected, and data cleaning has occurred.

Site has been used as a stratification in the randomisation, Site will be accounted for in all analyses by including site as a random effect. A fixed effect for the stratification factor of paternal asthma will be included in all analyses.

For the analysis of each outcome, the following information will be presented:

- The number of patients included in each analysis, by treatment group.
- A summary statistic of the outcome (e.g. mean (SD), number (%), by treatment group
- The estimated treatment effect
- A 95% confidence interval for the estimated treatment effect
- A two-sided p-value

Statistical significance will be assessed at the 5% level.

14.5 SUMMARY OF BASELINE DATA AND FLOW OF PARTICIPANTS

Baseline characteristics and clinical data will be summarised by treatment group. Numbers (%) for categorical variables and means (SD) or medians (IQR) for continuous variables as appropriate will be provided separately for each group. Participant flow through the trial will be illustrated by a CONSORT flow diagram [33].

14.6 Analysis of Participant Populations

The intention-to-treat population consists of all randomised children with a recorded outcome analysed according to the treatment to which they were randomised.

14.7 PRIMARY OUTCOME ANALYSIS

The primary analysis will be conducted on the ITT population.

The primary outcome of parent-reported, healthcare professional-confirmed, wheeze between 19 and 24 months will be analysed using a mixed-effect logistic regression model. The magnitude of the treatment effect will be reported as an odds ratio with a 95% confidence interval. Significance will be set at p<0.05.

Only site and parental asthma will be accounted for in the analysis, no other important covariates have been identified. Should any variables of interest be identified in the scientific literature during the course of the trial their analysis will be considered exploratory and detailed in the SAP.

The primary analysis will be repeated on the compliant population, defined as those who take at least 80% of the assigned medication over the 24 months of treatment, evidenced by the parent-reported monthly questionnaire.

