2.5.3 Exploratory Endpoints

- 1. Impact of BV on parent reported clinical outcome measures associated with wheeze and atopy across the whole 24 months:
- Time in days to first episode of wheeze from initiation of IMP or placebo
- Number of unscheduled medical attendances for wheeze
- Number of hospital admissions for wheeze
- Number of days admitted to hospital for wheeze
- Number of unscheduled medical attendances for any lower respiratory symptoms
- Number of courses of systemic corticosteroids (within the 24 months post initiation of IMP or placebo)
- Number of courses of oral corticosteroids for wheeze
- Number of courses of antibiotics
- Prescription of regular oral montelukast (yes/no)
- Eczema (yes/no)
- Other atopy related factors: breastfeeding (yes/no), food allergies, pet exposure, smoke exposure
- 2. To understand patterns in compliance across treatment groups and the effect of compliance on the treatment effect.
- Compliance with medication assessed from returned treatment diaries completed by parents and guardians.
- The effect of oral BV on parent-reported, healthcare-professional confirmed wheeze in the stratum of patients that have met compliance as defined as 80% of capsules taken across the whole 24 months.
- 3. Parents and healthcare professionals' self-assessment of blinding:
- Parent prediction: BV or placebo

- Healthcare professional prediction: BV or placebo
- 4. Two optional blood samples collected at trial entry, 12 months and 24 months (end of the treatment period):
- Blood serum total and specific IgE to aeroallergens, and blood eosinophil count

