7.2 RANDOMISATION METHOD

Randomisation will be performed by an authorised member of the research team at the site using the web-based randomisation service, developed and managed by Sealed Envelope (https://www.sealedenvelope.com/). Eligibility and consent will be verified (see Sections 4-6) before each child is randomised. Children will be allocated into two arms (oral BV and placebo) in a 1:1 ratio.

Randomisation will be stratified by site and parental asthma and the lists generated using random blocks of size 4 and 6. Site was chosen as a stratification factor to allow for potential differences in patient outcomes across sites, due to the characteristics of participants in different geographical locations or the characteristics of the sites themselves. Parental asthma was chosen as a stratification factor since it is a known risk factor for the development of recurrent wheeze [29].

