10.7 Assessment of compliance

Parents or guardians will self-report their child's adherence by keeping a treatment diary (or equivalent recording method) and reporting the number of doses taken in the monthly questionnaire. An individual child is said to be compliant if they take at least 80% of the number of IMP capsules. Non-compliance will prompt a reminder to support improving compliance going forwards. Reasons for missed doses will be collected from parents or guardians and an assessment will be made as to whether the reasoning constitutes non-compliance.

If a child is deemed non-compliant, the child will remain in the trial and followed up by the trial team at intervals via text, telephone and email to provide additional support. The site research team will monitor the completion of the monthly questionnaire to identify non-responsive participants. We understand that there can be a lot of changes in families with a young child(ren) so we will make efforts to support and empower parents to participate. Our study will have an open door approach to allow parents and guardians to resume participation after a non-responsive period.

Participants will be reminded of the dosing schedule at the monthly questionnaire. Parents or guardians will be provided with a treatment diary "treatment medication record sheet" for their optional use. This will act as both a reminder for them to take the treatment on a given day and will ask them to tick off that this was indeed done to record compliance.

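### The rerun of the primary analysis in children taking at least 80% of doses gives the compliant-stratum effect only under an unstated assumption; label it supportive and add a randomisation-based complier estimate.

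*Protocol*

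**What the plan says.** Section 14.7 makes the ITT analysis primary: a mixed-effect logistic model for wheeze in months 19 to 24 that accounts only for site and parental asthma. It then adds: "The primary analysis will be repeated on the compliant population, defined as those who take at least 80% of the assigned medication". The threshold applies to the full treatment period, and the evidence named is the questionnaire that parents complete each month. The section does not label this rerun supportive or exploratory.

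The aim behind it is exploratory. Section 2.4.1 asks how compliance affects the treatment effect. Section 2.5.3 words the endpoint as the effect of BV "in the stratum of patients that have met compliance as defined as 80% of capsules taken across the whole 24 months".

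The data source differs between sections. Section 2.5.3 has "Compliance with medication assessed from returned treatment diaries completed by parents and guardians", whereas the summary table in section 2.6 and section 14.7 use the monthly questionnaire. Section 10.7 makes the diary optional. It also says of reasons for missed doses that "an assessment will be made as to whether the reasoning constitutes non-compliance", beside its own 80% rule.

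**The concern.** Randomisation makes the two whole arms comparable. It does not do so for the two groups of compliers, because who complies is settled afterwards. Section 8 lists reasons for stopping that can depend on arm or prognosis: adverse events, allergic reaction, concomitant illness and parental request. If wheeze-prone children stop more readily in one arm, the compliers differ in risk before any drug effect, and a model with only site and parental asthma does not remove that difference.

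Timing adds to this. Doses count to month 24 and the outcome is counted in months 19 to 24, so illness in the window can cost doses and move a child out of the analysed set.

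At stake is the reading of a secondary result. An odds ratio in compliers, reported directly under the primary outcome, invites the interpretation that it is the effect when the drug is taken.

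**Working it through.** **1. The plan's own figure.** Inputs from section 14.1: "our effect size is based on a reduction of 40% of the number of children developing parent-reported doctor-confirmed wheeze (22% to 13.2"%), 90% power, 5% significance. Section 14.4 gives two-sided testing and section 7.2 gives 1:1 allocation. With unpooled variance, n per arm = (1.960 + 1.282)² × (0.22×0.78 + 0.132×0.868) / 0.088² = 388.3, so 389 per arm and 778 in total, as stated. Also 894 − 116 = 778. The planned ITT difference is 22 − 13.2 = 8.8 points.

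**2. Null drug effect, two risk classes (assumed).** Half the children have 30% risk and half 14%, so 22% overall. Complier risk in an arm = (cH×0.30 + cL×0.14)/(cH + cL), where cH and cL are compliance in the high- and low-risk halves. In rows 2 to 4 placebo compliance is 70%/70%, so placebo complier risk is 22.0%.

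| Placebo cH/cL | BV cH/cL | BV complier risk | Compliant-only OR | Two-sided rejection |
|---|---|---|---|---|
| 60%/80% | 60%/80% | 20.9% (placebo also 20.9%) | 1.00 | 5.0% |
| 70%/70% | 60%/80% | 0.292/1.4 = 20.9% | 0.934 | 6.2% |
| 70%/70% | 50%/80% | 0.262/1.3 = 20.2% | 0.895 | 8.1% |
| 70%/70% | 80%/60% | 0.324/1.4 = 23.1% | 1.068 | 6.2% |

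The ITT odds ratio is 1.00 in every row.

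**3. Null drug effect, continuous risk (assumed).** Logit risk = −1.55 + s with s standard normal, so 21.4% risk in both arms. Logit compliance = 1.0 + b×s, integrated over s.

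| b placebo | b BV | Complier risk, placebo vs BV | OR |
|---|---|---|---|
| −0.8 | −0.8 | 18.2% vs 18.2% | 1.00 |
| −0.5 | −0.4 | 19.4% vs 19.8% | 1.03 |
| −0.8 | −0.6 | 18.2% vs 19.0% | 1.05 |
| −0.8 | −0.2 | 18.2% vs 20.6% | 1.17 |
| −0.2 | −0.8 | 20.6% vs 18.2% | 0.86 |

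In the last two rows overall compliance is about 71% in one arm and 73% in the other, so comparing compliance rates would not reveal the problem. Rejection is about 11% there.

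**4. A true effect.** Take risk ratio 0.6 in BV compliers, no effect otherwise, BV compliance 50%/80% and placebo 70%/70%. BV complier risk is 0.6 × 0.2015 = 0.1209. The subset difference is 0.1209 − 0.22 = −0.099. The true stratum effect is 0.1209 − 0.2015 = −0.081. The ITT difference is −0.0524, and divided by BV compliance (0.65) it returns −0.081.

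**5. Size of a complier-average estimate.** With ITT difference 8.8 points, compliance c, and non-compliers receiving a fraction f of the effect: complier effect = 8.8/[c + f(1 − c)]. At an assumed c = 0.70, f = 0 gives 8.8/0.70 = 12.6 points and f = 0.5 gives 8.8/0.85 = 10.4. With f = 0 and c from 0.50 to 0.90 it runs from 17.6 to 9.8.

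**6. Overlap with the outcome window.** The course is 10 × 24 = 240 doses and 80% is 192. Months 19 to 24 hold 60 doses. A child fully dosed to month 18 has 180 and must miss more than 48 of the last 60 to fall below 192. A child with 150 must take 42 of 60. Below 132 (192 − 60) the child cannot reach the cut.

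**The case against.** The strongest defence is that selection may well be equal. Placebo capsules match in shape, colour and size (section 10.1), families and site staff are blinded (section 7.5), and the infant trials cited in section 1.3.4 suggest similar tolerability. With equal selection the subset estimate is unbiased, as the first row of each table shows. This stands. A reader might infer that the rerun cannot estimate the compliant-stratum effect at all; the documents do not support that. What is missing is the assumption under which it does.

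The odds ratios of 0.86 and 1.17 need illness to drive non-compliance four times as strongly in one blinded arm as in the other. No figure in the protocol supports that pattern; milder differences give 1.03 to 1.05. They mark a range and do not predict a bias.

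A reader might also infer that wheeze in the window routinely removes children. Section 10.12 lets missed doses be made up by extending the course within the month, and step 6 shows that the overlap matters mainly for children already near the cut.

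Nor does section 10.7 say that its assessment of reasons overrides the 80% rule. It sits among reminders and family support, and section 14.7 defines the analysis set by number. Likewise, section 14.7 already names the questionnaire, so the analysis source is fixed; section 2.5.3 is the outlier.

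Finally, the SAP may name a causal method. That is possible, but the protocol itself fixes the subset rerun and places it under the primary outcome without a label.

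**Conclusion.** The point holds in a limited form. The rerun conditions on a post-randomisation, parent-reported variable that overlaps the outcome window. It identifies the effect in the compliant stratum only if the same kind of child complies in both arms, which the protocol does not state. A single subset odds ratio also does not answer the section 2.4.1 question of how compliance changes the effect.

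The size depends on assumed compliance patterns: with no drug effect, a compliant-only odds ratio of 1.00 under equal selection and about 0.86 to 1.17 under strongly unequal selection. It would be wrong to infer that the trial's main result is at risk, since ITT is primary and the compliance aim is exploratory. This is an inexpensive improvement to a secondary analysis.

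**What to change.** - In section 14.7, label the compliant-subset rerun supportive and exploratory, and state the assumption that compliers are comparable between arms.
- Add a complier-average causal effect with randomisation as the instrument, on the risk-difference scale, adjusted for site and parental asthma. BV is not licensed in the UK (section 10.2), so placebo children should have little access to it.
- Lead with a version based on the number of doses taken. Present a binary 80% version only with its assumption stated and varied, because a child with 191 of 240 doses has plainly received drug.
- Add a sensitivity version counting doses to month 18, before the outcome window opens, keeping the 24-month definition as the main one.
- Align section 2.5.3 with sections 2.6 and 14.7 on the monthly questionnaire as source, and say that the section 10.7 review of reasons does not change the analysis set.

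The cost is protocol or SAP wording and one short analysis on data already collected, best settled before unblinding. The drawback is wider confidence intervals and reliance on the exclusion assumption, that allocation affects wheeze only through the doses taken, which the data cannot fully check.

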14.8 SECONDARY OUTCOME ANALYSIS

14.8.1 Secondary Outcomes

The analysis of secondary outcomes will be conducted on the ITT population. Binary outcomes will be analysed using a mixed effects logistic regression model and will be presented as an odds ratios (95% CI). Count outcomes will be analysed using a mixed effects negative binomial regression model to account for overdispersion and will be presented as a rate ratio (95% CI). Time to event outcomes will be analysed using a frailty model and will be presented as a hazard ratio (95% CI).

